1. DIAGNOSIS VERSUS SIGNS AND SYMPTOMS

1.1. INFUSION-RELATED REACTIONS

Adverse events that occur during or after study drug administration and are judged to be related to study treatment infusion should be captured as a diagnosis (e.g., infusion-related reaction [IRR]) on the Adverse Event eCRF. If possible, avoid ambiguous terms such as “systemic reaction.” Associated signs and symptoms should be recorded on the dedicated Infusion-Related Reaction eCRF. If a participant experiences both a local and systemic reaction to the same dose of study drug, each reaction should be recorded separately on the Adverse Event eCRF, with signs and symptoms also recorded separately on the dedicated Infusion-Related Reaction eCRF.

1.2. OTHER ADVERSE EVENTS

For AEs other than IRRs (see Section 1.1), a diagnosis (if known) should be recorded on the Adverse Event eCRF rather than individual signs and symptoms (e.g., record only liver failure or hepatitis rather than jaundice, asterixis, and elevated transaminases). However, if a constellation of signs and/or symptoms cannot be medically characterized as a single diagnosis or syndrome at the time of reporting, each individual event should be recorded on the Adverse Event eCRF. If a diagnosis is subsequently established, all previously reported AEs based on signs and symptoms should be nullified and replaced by one AE report based on the single diagnosis, with a starting date that corresponds to the starting date of the first symptom of the eventual diagnosis.

2. ADVERSE EVENTS OCCURRING SECONDARY TO OTHER EVENTS

In general, AEs occurring secondary to other events (e.g., cascade events or clinical sequelae) should be identified by their primary cause, with the exception of severe or serious secondary events. However, medically significant AEs occurring secondary to an initiating event that are separated in time should be recorded as independent events on the Adverse Event eCRF. For example:

- If vomiting results in mild dehydration with no additional treatment in a healthy adult, only vomiting should be reported on the eCRF.
- If vomiting results in severe dehydration, both events should be reported separately on the eCRF.

- If a severe gastrointestinal hemorrhage leads to renal failure, both events should be reported separately on the eCRF.
- If dizziness leads to a fall and subsequent fracture, all three events should be reported separately on the eCRF.

All AEs should be recorded separately on the Adverse Event eCRF if it is unclear as to whether the events are associated.

3. PERSISTENT OR RECURRENT ADVERSE EVENTS

A persistent AE is one that extends continuously, without resolution, between participant evaluation time-points. Such events should only be recorded once on the Adverse Event eCRF. The initial severity of the event should be recorded, and the severity should be updated to reflect the most extreme severity any time the event worsens. If the event becomes serious, the Adverse Event eCRF should be updated to reflect this.

A recurrent AE is one that resolves between participant evaluation time-points and subsequently recurs. Each recurrence of an AE should be recorded separately on the Adverse Event eCRF.

4. ABNORMAL LABORATORY VALUES

Not every laboratory abnormality qualifies as an adverse event. A laboratory test result should be reported as an adverse event if it meets any of the following criteria:

- Accompanied by clinical symptoms.
- Results in a change in study treatment (e.g., dosage modification, treatment interruption, or treatment discontinuation).
- Results in a medical intervention (e.g., potassium supplementation for hypokalemia) or a change in concomitant therapy.
- Clinically significant in the Investigator's judgment.

It is the Investigator's responsibility to review all laboratory findings. Medical and scientific judgment should be exercised in deciding whether an isolated laboratory abnormality should be classified as an adverse event.

If a clinically significant laboratory abnormality is a sign of a disease or syndrome (e.g., alkaline phosphatase and bilirubin 5 times the upper limit of normal [ULN] associated with cholecystitis), only the diagnosis (i.e., cholecystitis) should be recorded on the Adverse Event eCRF.

If a clinically significant laboratory abnormality is not a sign of a disease or syndrome, the abnormality itself should be recorded on the Adverse Event eCRF, along with a descriptor indicating if the test result is above or below the normal range (e.g., "elevated potassium", as opposed to "abnormal potassium"). If the laboratory abnormality can be characterized by a precise clinical term per standard definitions, the clinical term should be recorded as the AE. For example, an elevated serum potassium level of 7.0 mEq/L should be recorded as "hyperkalemia."

Observations of the same clinically significant laboratory abnormality from visit to visit should not be repeatedly recorded on the Adverse Event eCRF, unless the etiology changes. The initial severity of the event should be recorded, and the severity or seriousness should be updated any time the event worsens.

5. ABNORMAL VITAL SIGN VALUES

Not every vital sign abnormality qualifies as an AE. A vital sign result should be reported as an AE if it meets any of the following criteria:

- Accompanied by clinical symptoms.
- Results in a change in study treatment (e.g., dosage modification, treatment interruption, or treatment discontinuation).
- Results in a medical intervention or a change in concomitant therapy.
- Clinically significant in the Investigator's judgment.

It is the Investigator's responsibility to review all vital sign findings. Medical and scientific judgment should be exercised in deciding whether an isolated vital sign abnormality should be classified as an adverse event.

If a clinically significant vital sign abnormality is a sign of a disease or syndrome (e.g., high blood pressure), only the diagnosis (i.e., hypertension) should be recorded on the Adverse Event eCRF.

Observations of the same clinically significant vital sign abnormality from visit to visit should not be repeatedly recorded on the Adverse Event eCRF, unless the etiology changes. The initial severity of the event should be recorded, and the severity or seriousness should be updated any time the event worsens.

6. ABNORMAL LIVER FUNCTION TESTS

The finding of an elevated ALT or AST ($> 3 \times \text{ULN}$) in combination with either an elevated total bilirubin ($> 2 \times \text{ULN}$) or clinical jaundice in the absence of cholestasis or other causes of hyperbilirubinemia is considered to be an indicator of severe liver injury.

Therefore, Investigators must report as an adverse event the occurrence of either of the following:

- Treatment-emergent ALT or AST $> 3 \times$ ULN in combination with total bilirubin $> 2 \times$ ULN.
- Treatment-emergent ALT or AST $> 3 \times$ ULN in combination with clinical jaundice.
- For participants who have liver metastases or are receiving hepatotoxic concomitant medications, Investigators must report as an AE the occurrence of either of the following:
 - Treatment-emergent ALT or AST $> 5 \times$ ULN value in combination with total bilirubin $> 2 \times$ ULN (of which $\geq 35\%$ is direct bilirubin).
 - Treatment-emergent ALT or AST $> 5 \times$ ULN value in combination with clinical jaundice.

The most appropriate diagnosis or (if a diagnosis cannot be established) the abnormal laboratory values should be recorded on the Adverse Event eCRF (see [Appendix 2](#)) and reported to the Sponsor immediately (i.e., no more than 24 hours after learning of the event), either as an SAE or a non-serious adverse event of special interest (Section [8.3.6](#)).

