7.1.2 Temporary Interruption

Before permanently discontinuing study treatment (regardless of whether initiated by the participant, the Investigator, or Sponsor), an interruption should be considered. Participants who have temporarily interrupted study treatment should be considered to restart as soon as medically justified in the opinion of the Investigator.

Study treatment may be temporarily suspended for up to 12 weeks to allow for resolution of toxicity to NCI CTCAE Grade ≤ 2 for hematological toxicities or Grade ≤ 1 for non-hematological toxicities (with the exception of a toxicity considered as non-study treatment related). If study treatment is withheld for > 12 weeks, the participant will be discontinued from study treatment.

Dose interruptions for reason(s) other than toxicity, such as surgical procedures, may be allowed, and the acceptable length of interruption should be discussed between the Investigator and the Medical Monitor. Minor elective surgery will generally be permitted during the study with resumption of treatment as soon as possible post-procedure, assuming normal recovery. This can be done to avoid the discontinuation of participants who could potentially benefit from study treatment.

It should be noted that infusions/cycles not occurring at the anticipated schedule, are considered as delayed, not missed.

If a participant has a complete response (CR) or achieves maximum clinical benefit as determined by the Investigator and the Sponsor after an integrated assessment of radiographic data, biopsy results (if available), and clinical status, the study treatment may be paused at the discretion of the Investigator after discussion with the Medical Monitor. While the treatment is paused, assessments per SoA (Section 1.3) will be suspended, except for tumor assessments. The length of the treatment pause is to be included in the calculation of the maximum treatment period duration (24 months from C1D1 to discontinuation visit), as per Section 4.1.

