8.2.7 Clinical Safety Laboratory Assessments

Normal ranges for the study laboratory parameters must be supplied to the Sponsor before the study starts.

A list of clinical laboratory tests to be performed is provided in [Appendix 4](#) and these assessments must be conducted in accordance with the separate laboratory manual and the SoAs (Section [1.3](#)).

The Investigator must review the laboratory report, document this review, and record any clinically relevant changes occurring during the study in the AE section of the CRF. The laboratory reports must be filed with the source documents. Clinically significant abnormal laboratory findings are those, which are not associated with the underlying disease, unless judged by the Investigator to be more severe than expected for the participant's condition.

- In the event of unexplained abnormal clinically significant laboratory test values, the tests should be repeated immediately and followed up until they have returned to the normal range and/or an adequate explanation of the abnormality is found.
- If such values do not return to normal/baseline within a period judged reasonable by the Investigator, the etiology should be identified and the Sponsor notified.
- If laboratory values from non-protocol-specified laboratory assessments performed at the local laboratory require a change in participant management or are considered clinically significant by the Investigator (e.g., SAE, AE, or dose-modification), then the results must be recorded in the CRF.

Results of clinical laboratory testing will be recorded on the eCRF or be received as electronically produced laboratory reports submitted directly from the local or central laboratory.

Additional blood or urine samples may be taken at the discretion of the Investigator if the results of any test fall outside the reference ranges or clinical symptoms necessitate additional testing to monitor participant safety.

Where the clinical significance of abnormal laboratory results at screening is considered uncertain, screening laboratory tests may be repeated prior to randomization to confirm eligibility.

Based on continuous analysis of the data in this study and other studies, any sample type not considered to be critical for safety may be stopped at any time if the data from the samples collected do not produce useful information.

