8.3.7.2 Immune-mediated Adverse Events

Most imAEs observed with CPIs have been mild and self-limiting, however, such events should be recognized early and treated promptly to avoid potentially major complications. Any organ or tissue can be involved, although some imAEs occur much more commonly than do others. The most frequently occurring imAEs affect the skin, colon, endocrine organs, liver, and lungs. Others are very infrequent but may be very serious, even lethal, such as neurological disorders and myocarditis.

Discontinuation of study treatment may not have an immediate therapeutic effect, and in severe cases, immune-mediated toxicities may require acute management with topical corticosteroids, systemic corticosteroids, mycophenolate, or TNF- α inhibitors. Study treatment may be suspended for most Grade 2 toxicities, with consideration of resuming when symptoms revert to Grade 1 or less. Corticosteroids may be administered. Grade 3 toxicities generally warrant suspension of study treatment and the initiation of high-dose corticosteroids (prednisone, 1-2 mg/kg/day, or methylprednisolone, 1-2 mg/kg/day). Corticosteroids should be tapered over the course of at least 4 to 6 weeks. Some

refractory cases may require infliximab or other immunosuppressive therapy. In general, permanent discontinuation of study treatment is recommended with Grade 4 toxicities, with the exception of endocrinopathies that have been controlled by hormone replacement. The management guidelines for imAEs associated with study treatment are provided in [Appendix 7](#).

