^a Study drug may be withheld for a longer period (i.e., > 12 weeks after event onset) to allow for corticosteroids (if initiated) to be reduced to ≤ 10 mg/day oral prednisone or equivalent. The acceptable length of the extended period must be based on the assessment of benefit-risk by the Investigator and in alignment with the protocol requirement for duration of treatment and documented by the Investigator. The Medical Monitor will be available to advise as needed.

^b If corticosteroids have been initiated, they must be tapered over ≥ 1 month to ≤ 10 mg/day oral prednisone or equivalent before study drug can be resumed.

HEPATIC EVENTS

Immune-mediated hepatitis may be associated with the administration of study drug. Eligible patients must have adequate liver function, as manifested by measurements of total bilirubin and hepatic transaminases, and liver function will be monitored throughout study treatment. Management guidelines for hepatic events are provided in [Table 2](#).

Participants with right upper-quadrant abdominal pain and/or unexplained nausea or vomiting should have liver function tests (LFTs) performed immediately and reviewed before administration of the next dose of study drug.

For participants with elevated LFTs, concurrent medication, viral hepatitis, and toxic or neoplastic etiologies should be considered and addressed, as appropriate.

Table 2 Management Guidelines for Hepatic Events

Event	Management
Hepatic event, Grade 1	
• Continue study drug.• Monitor LFTs until values resolve to within normal limits or to baseline values.
Hepatic event, Grade 2	
All events:
 
• Monitor LFTs more frequently until return to baseline values. 
Events of > 5 days' duration:
 
• Withhold study drug for up to 12 weeks after event onset.^a• Initiate treatment with 1–2 mg/kg/day oral prednisone or equivalent.• If event resolves to Grade 1 or better, resume study drug.^b• If event does not resolve to Grade 1 or better while withholding study drug, permanently discontinue study drug and contact Medical Monitor.

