Hepatic event, Grade 3 or 4	
• Permanently discontinue study drug and contact Medical Monitor.• Consider patient referral to gastrointestinal specialist for evaluation and liver biopsy to establish etiology of hepatic injury.• Initiate treatment with 1–2 mg/kg/day oral prednisone or equivalent.• If event does not improve within 48 hours after initiating corticosteroids, consider adding an immunosuppressive agent. 
If event resolves to Grade 1 or better, taper corticosteroids over ≥ 1 month.

Event	Management
In participants with liver lesions	
AST/ALT is within normal limits at baseline and increases to $> 3 \times \text{ULN}$ to $\leq 10 \times \text{ULN}$ or AST/ALT is $> \text{ULN}$ to $\leq 3 \times \text{ULN}$ at baseline and increases to $> 5 \times \text{ULN}$ to $\leq 10 \times \text{ULN}$ or AST/ALT is $> 3 \times \text{ULN}$ to $5 \times \text{ULN}$ at baseline and increases to $> 8 \times \text{ULN}$ to $\leq 10 \times \text{ULN}$	Monitor LFTs more frequently until return to baseline values. 
 Withhold study drug for up to 12 weeks after event onset^a. Events of > 5 days' duration: 
 Consider initiating treatment with 1–2 mg/kg/day prednisone or equivalent. If event resolves to baseline, resume study drug^b. If event does not resolve to baseline while withholding study drug, permanently discontinue study drug and contact Medical Monitor.
AST or ALT increases to $> 10 \times \text{ULN}$ or total bilirubin increases to $> 3 \times \text{ULN}$	
 Permanently discontinue study drug and contact Medical Monitor Consider patient referral to GI specialist for evaluation and liver biopsy to establish etiology of hepatic injury. Initiate treatment with 1–2 mg/kg/day prednisone or equivalent If event does not improve within 48 hours after initiating corticosteroids, consider adding an immunosuppressive agent. If event resolves to baseline, taper corticosteroids over ≥ 1 month.

ALT = alanine aminotransferase; AST = aspartate aminotransferase; CTCAE = Common Terminology Criteria for Adverse Events; GI = Gastrointestinal; LFT = Liver function test; NCI = National Cancer Institute; ULN = Upper limit of normal.

Note: Management guidelines are presented by adverse event severity based on NCI CTCAE and are applicable to both CTCAE Version 4.0 and CTCAE Version 5.0.

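### The hepatic dosing table (Appendix 7, Table 2) has no action keyed to the combined transaminase-plus-bilirubin finding of Appendix 3, so a hold rests on judgment in two narrow situations

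*Combined protocol and SAP*

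**What the plan says.** Appendix 3, Section 6 defines a reportable combination: treatment-emergent ALT or AST > 3 x ULN with total bilirubin > 2 x ULN or clinical jaundice. With liver metastases or hepatotoxic co-medication, the ALT/AST limit is > 5 x ULN, and at least 35% of the bilirubin must be direct unless jaundice is the second component. The protocol's reading is that the combination, "in the absence of cholestasis or other causes of hyperbilirubinemia is considered to be an indicator of severe liver injury". The stated consequence is a report to the Sponsor within 24 hours. Section 8.3.6 lists the finding as a non-serious event of special interest and also sets no dosing action.

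Dosing is governed by Appendix 7, Table 2:

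- **Graded rows.** Grade 1 continues. Grade 2 asks sites to "Monitor LFTs more frequently until return to baseline values" and withholds drug only once the event has lasted more than 5 days. Grade 3 or 4 is permanent discontinuation.
- **Liver-lesion rows.** Drug is withheld at once for ALT/AST > 3 to 10 x ULN from a normal baseline, > 5 to 10 x ULN from a baseline above ULN and up to 3 x ULN, and > 8 to 10 x ULN from a baseline of > 3 to 5 x ULN. Drug is permanently discontinued if ALT or AST exceeds 10 x ULN "or total bilirubin increases to" more than 3 x ULN.

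No row combines the two measurements, and none mentions jaundice.

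**The concern.** The protocol names a signal of possible severe liver injury in one appendix and decides dosing in another that never refers to it. A site following Table 2 literally could therefore give the dose due on the day the signal appears. Section 6.6 bars dose reductions, so a hold is the only reversible protection.

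The table is also uneven. With liver lesions and a normal baseline, an isolated ALT rise above 3 x ULN is withheld at once. Without liver lesions, the combined finding waits 5 days if it is graded 2.

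At stake is participant safety around one or a few doses.

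**Working it through.** **Inputs.** The reporting limits are from Appendix 3, Section 6, and the action limits from Appendix 7, Table 2. The entry ceiling is ALT/AST of at most 5 x ULN with liver metastases (Section 5.1, criterion 12). Dosing is every 14 days, -1/+3 days (Section 1.3, Table 1). Safety assessments up to 72 hours old are accepted (Section 8.2). I treat liver metastases in Appendix 3 and liver lesions in Table 2 as the same group.

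**Situation (a): liver lesions.** I crossed 3 baseline tiers, 3 on-treatment ALT/AST bands (> 5 to 8, > 8 to 10, > 10 x ULN) and 3 bilirubin states (jaundice at <= 2, > 2 to 3, > 3 x ULN). That gives 3 x 3 x 3 = 27 reportable cells.

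| Baseline ALT/AST | Discontinue | Withhold | No liver-lesion row |
|---|---|---|---|
| Normal | 5 | 4 | 0 |
| > 1 to 3 x ULN | 5 | 4 | 0 |
| > 3 to 5 x ULN | 5 | 2 | 2 |
| Total | 15 | 10 | 2 |

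In each tier the 5 discontinue cells are the 3 with ALT/AST > 10 x ULN plus the 2 others with bilirubin > 3 x ULN. The two unmatched cells have baseline > 3 to 5 x ULN and on-treatment > 5 to 8 x ULN, with bilirubin > 2 to 3 x ULN or with jaundice at <= 2 x ULN.

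Example: ALT goes from 4 to 7 x ULN and bilirubin is 2.5 x ULN, at least 35% direct. Appendix 3 is met (7 > 5; 2.5 > 2). No liver-lesion row is met (7 <= 8; 2.5 <= 3).

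Fold-rise covered by the gap:

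- from just above 3 x ULN: 5/3 = 1.67 to 8/3 = 2.67
- from 4 x ULN: 5/4 = 1.25 to 8/4 = 2.0
- from 5 x ULN: 5/5 = 1.0 to 8/5 = 1.6

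What follows depends on a point Table 2 leaves open. If the liver-lesion rows replace the graded rows, no hold is required while values stay in this band. If the graded rows also apply, Grade 2 is held after 5 days and Grade 3 or 4 is discontinued.

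**Situation (b): no liver lesions, event graded 2.** The CTCAE limits for liver tests are not printed, so the grade is an assumption. Date onset at the first abnormal sample. A pre-dose sample is at most 72 h = 3 days old. Since 3 < 5, a hold is not yet required. The next dose falls 14 - 1 = 13 to 14 + 3 = 17 days later. Since 13 > 5, it is withheld if the event is unresolved. The exposure is at most one dose. By grade, the range is: Grade 1 continue, Grade 2 one further dose, Grade 3 or 4 permanent discontinuation.

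**Do other sections require a hold?**

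- Section 7.1.2 is permissive: "Study treatment may be temporarily suspended for up to 12 weeks to allow for resolution of toxicity".
- Section 8.3.7.2 is permissive: "Study treatment may be suspended for most Grade 2 toxicities, with consideration of resuming when symptoms revert to Grade 1 or less".
- Section 8.2.7 requires that, for unexplained clinically significant values, "the tests should be repeated immediately and followed up until they have returned to the normal range" or are explained. That is testing, not holding.
- The hepatic text of Appendix 7 says "toxic or neoplastic etiologies should be considered and addressed, as appropriate". That is work-up, not holding.
- The opening of Appendix 7 asks the Investigator to weigh benefit against risk before giving more drug. Section 8 sends immediate safety concerns to the Sponsor. Sections 7.1 and 8.3.7 rest on judgment. None of these carries a liver threshold.

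A hold is permitted throughout, but none of these provisions mandates one for this finding.

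**The case against.** The strongest reply is that dosing here already follows a judgment procedure with Sponsor involvement. Laboratory results must be available before treatment, benefit-risk must be weighed before more drug is given, the event is reported within 24 hours, and Section 7.1 makes discontinuation mandatory for any condition that may endanger the participant. This stands as far as it goes: a careful site would probably hold. It does not supply a rule, and the specific Grade 2 instruction in Table 2 points the other way for the first 5 days.

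Second, neither situation is fully fixed by the text. Situation (a) leaves the hold to judgment throughout only if the liver-lesion rows displace the graded ones. Situation (b) needs a Grade 2 event. Sites record a diagnosis rather than separate signs where they can (Appendix 3, Section 1.2). For terms outside CTCAE, the Appendix 2 scale makes a severe or medically significant event Grade 3, which means discontinuation. Both points stand, so (b) is neither proved nor excluded.

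Third, an automatic hold on the reporting trigger would catch tumour-related rises and stable Gilbert bilirubin. Section 2.3 gives a median OS of 8.3 to 10.9 months with PD1 inhibitors, so a 12-week hold is a real cost. This stands and shapes the fix.

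**Conclusion.** The gap is real but narrow. Table 2 has no action keyed to the combined finding, and a hold is left to judgment in (a) and (b). Situation (a) is 2 of 27 unweighted cells, both in one baseline tier (2 of its 9), and depends on how the liver-lesion and graded rows relate. Situation (b) is at most one dose and depends on an assumed Grade 2. The documents give no event rate, so the number of participants affected is not estimated.

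A reader might infer that participants with probable severe liver injury would routinely stay on drug, or that the two appendices contradict each other. The documents support neither. With liver lesions, 25 of the 27 cells already lead to a hold or discontinuation. Without them, Grade 3 or 4 means discontinuation. Appendix 3 governs reporting and is silent on dosing, so there is an omission rather than a conflict. It also ties the finding to severe injury only when other causes are absent. Nothing here bears on the OS analysis or the comparison of arms. This is a minor participant-safety improvement, worth making because it is cheap.

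**What to change.** Add one row to Appendix 7, Table 2, for participants with and without liver lesions.

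- **Trigger.** The Appendix 3, Section 6 criterion is met, with its > 5 x ULN and 35% direct-bilirubin qualifiers where they apply, and the bilirubin elevation or jaundice is itself new or worse than at baseline. The last condition keeps stable Gilbert bilirubin, admitted up to 3 x ULN, from triggering a hold.
- **Action.** Withhold from first detection without the 5-day wait, contact the Medical Monitor and evaluate the cause.
- **Release.** If cholestasis, tumour or another cause is documented, dosing may resume under the existing rows after a recorded benefit-risk decision with the Medical Monitor. If not, hold until transaminases and bilirubin recover to the existing Table 2 targets (Grade 1 or better, or baseline with liver lesions).

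Also state whether the graded rows apply to participants with liver lesions. Leave unchanged the existing discontinuation rows and the > 8 x ULN tier for isolated rises.

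**Cost.** One row and one sentence in an amendment. No new test is needed: ALT, AST, and total and direct bilirubin are in the dosing-day chemistry panel, with results due before treatment. Some doses will be delayed pending work-up. In (b) this is usually one dose, because an unresolved Grade 2 event is already held after 5 days. In (a) it can reach 12 weeks, or 12 / 2 = 6 scheduled doses. Section 7.1.2 says that beyond "12 weeks, the participant will be discontinued from study treatment", but footnote a to Table 2 allows a longer hold for a corticosteroid taper, so six doses is not a firm ceiling. From a baseline of 5 x ULN, even a small ALT/AST rise with new bilirubin > 2 x ULN would trigger a hold.
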